7.2.5. Electrocardiogram

A single 12-lead ECG will be collected at screening and all other on-site visits as specified in the [Schedule of Activities](#). ECGs reading will be performed by a central reader.

All scheduled ECGs should be performed after the subject has rested quietly for at least 10 minutes in a supine position.

A subject's screening ECG must be within normal limits prior to randomization.

7.2.6. Special Safety Assessment

In the event of a suspected opportunistic infection, effort should be made to identify the pathogen utilizing laboratory or other methods appropriate to the clinical situation.

In case of a suspected viral skin infection (eg, herpes zoster and herpes simplex) or eczema herpeticum, a specimen for viral DNA may be analyzed locally for confirmation and results provided to the adjudication committee to support evaluation.

For subjects with a past history of oral or genital HSV and a presentation consistent to prior infections, further laboratory analysis may be performed at the discretion of the investigator.

7.3. Skin Type Assessment

As part of baseline characteristics, a skin type assessment will be done at the Day 1 visit using the Fitzpatrick Skin Type assessment (Refer to Appendix 5). This is used to classify a person's skin type by their response to sun exposure (ie, burning or tanning).

7.4. Assessment of Suicidal Ideation and Behavior

Subjects meeting exclusionary results as described in [Section 4.2](#) on the C-SSRS, SBQ-R and PHQ-8 should be excluded from participation; it is recommended the subject's primary care physician (PCP) should be informed, and the subject referred to a mental health professional, either by the PCP or the investigator according to their usual practice.

7.4.1. Columbia Suicide Severity Rating Scale (C-SSRS)

The Columbia Suicide Severity Rating Scale is a validated tool for investigative staff to use to evaluate suicidal ideation and behavior (Appendix 15).¹⁶ At the screening visit, if there are "yes" answers on items 4 or 5 in the past year or on any question in the suicidal behavior section of the C-SSRS in the past 5 years, the subject will not be included in the study. Trained site staff is to administer the C-SSRS to all subjects at screening and assess the subject's eligibility based on the answers.

7.4.2. Suicidal Behaviors Questionnaire-Revised (SBQ-R)

The Suicidal Behaviors Questionnaire-Revised (Appendix 16) is a patient-reported questionnaire consisting of 4 items to assess suicidal ideation, suicide attempts, threat of suicidal behavior, and likelihood of suicidal behavior. At the Screening Visit, if SBQ-R total score ≥ 8 , the subject will not be included in the study.³⁸ Site staff is to administer the SBQ-R to all subjects at screening and score immediately.

7.4.3. Patient Health Questionnaire – 8 Items (PHQ-8)

The Patient Health Questionnaire – 8 items (Appendix 17) is a patient-reported questionnaire consisting of 8 items to assess the subject's depression level. At Screening Visit, if PHQ-8 total score ≥ 15 , the subject will not be included in the study.³⁹ Site staff is to administer the PHQ-8 to all subjects at screening and score immediately.

7.5. Clinical Laboratory Tests

7.5.1. Blood Volume

Total blood sampling volume planned for this study is approximately 78 mL. Further details regarding the collection, processing, storage, and shipping of the blood samples will be provided in the lab manual.

7.5.2. Laboratory Tests

The following laboratory tests will be performed at time points identified in the [Schedule of Activities](#). Unscheduled clinical labs may be obtained at any time during the study to assess any perceived safety concerns at the investigator's discretion.

Sample collection, labeling, storage, and shipping information can be found in the laboratory manual. All laboratory tests with clinically important changes from baseline identified after administration of investigational product will be followed until the value stabilizes.

Subjects must abstain from all food and drink (except water and non-study medications) for an 8-hour overnight fast prior to labs that include the lipid profile panel on Day 1, Week 4, Week 12, and EOS. All other labs do not require fasting.

Laboratory Tests

Hematology	Serum Chemistry	Urinalysis	Other
Hemoglobin	BUN and Creatinine	pH	HIV ^a
Hematocrit	Creatine Phosphokinase	Glucose (qual)	HBsAg ^a
RBC count and indices (MCH, MCHC, MCV, RBC Morphology)	Glucose	Protein (qual)	HBcAb ^a
Reticulocyte count	Na+, K+, Cl-, Ca ⁺⁺	Blood (qual)	HBsAb ^b
Platelet count	Total CO2 (Bicarbonate)	Ketones	HCVAb ^a
WBC count with differential	AST, ALT	Nitrites	HCV RNA ^b
Total neutrophils (% Abs)	GGT	Leukocyte esterase	VZV IgG Ab ^g
Eosinophils (% Abs)	Total, Indirect & Direct Bilirubin	Microscopy and/or culture ^d	Serum FSH (WONCBP only) or Pregnancy Test ^{a, c}
Monocytes (% Abs)	Alkaline phosphatase		Urine pregnancy test ^e
Basophils (% Abs)	Lactate dehydrogenase		QFT-G or PPD (if applicable) ^e
Lymphocytes (% Abs)	Uric acid		HSV-1, HSV-2, VZV
Coagulation Panel	Albumin		
Activated Partial Thromboplastin Time (APTT) Prothrombin Time/International Normalized Ratio (PT/INR)	Total protein		
	Lipid Profile Panel ^f		
	Total cholesterol		
	LDL		
	HDL		
	Triglycerides		

a. At Screening only. HIV testing will be performed for all subjects.
 b. HBsAb reflex testing only if HBsAg negative but HBcAb positive. HCV RNA is reflex testing only if HCVAb is positive.
 c. Pregnancy testing for females of childbearing potential, including adolescents aged 12 years and older, regardless of whether they have experienced menarche; serum FSH for postmenopausal women who have been amenorrheic for at least 12 consecutive months.
 d. Microscopy with culture performed as appropriate.
 e. PPD results should be read within 48 to 72 hours.
 f. Lipid Profile Panel requires at least an 8 hour fast. Lipid profile panel will be completed at Day 1, Week 4, Week 12, and EOS, and will include total cholesterol, LDL, HDL, and triglycerides.
 g. Only for adolescents who do not have documentation of at least one dose of varicella vaccine.

Clinically significant abnormal findings should be recorded as AEs. Abnormal test results determined to be caused from laboratory error should not be reported as AEs. Clinically significant laboratory findings at the final assessment should be followed to resolution or until determined by the investigator to be stabilized. Repeat tests may be indicated to establish this. Refer to Appendix 4 for Guidelines on Monitoring and Discontinuation.

7.5.2.1. Hepatitis Testing

Hepatitis B testing: HB surface antigen (HBsAg), HB core antibody (HBcAb), HB surface antibody (HBsAb).

Interpretation of Hepatitis B Testing Results:

- HBsAg negative and HBcAb negative: Subject is eligible for the study;
- HBsAg positive and HBcAb negative: Subject is excluded from study participation;
- HBsAg negative and HBcAb positive and HBsAb positive: Subject is eligible for study;
- HBsAg negative and HBcAb positive and HBsAb negative: Subject is excluded from study participation.

Hepatitis C testing: Hepatitis C Antibody (HCV Ab), Hepatitis C Viral RNA (HCV RNA for confirmation of positive HCV Ab result).

Interpretation of Hepatitis C Testing Results:

- HCV Ab positive and HCV RNA positive: Subject is excluded from study participation.

7.5.2.2. Varicella Zoster Virus (VZV) IgG Antibody (Ab) Testing

Adolescent subjects without documented evidence of having received at least a single dose of the varicella vaccine in countries where the varicella vaccine is approved and standard of care will be tested for varicella zoster virus IgG Ab as described in the lab manual. Subjects that lack evidence of prior exposure to varicella zoster virus based on serological VZV IgG Ab testing are excluded.

7.5.2.3. Baseline Viral Screen

A serum sample will be collected at baseline but analyzed only if the subject has suspected varicella or herpes zoster. In that event, the sample would be analyzed for HSV1, HSV2 and VZV. Additional sample collection instructions will be provided in the lab manual ([Schedule of Activities](#)). The retained samples will be destroyed upon subject completion of this study or the long-term extension study.

7.6. Efficacy Assessments

7.6.1. Rater Qualifications

Clinical evaluations of atopic dermatitis will be performed by an experienced and qualified dermatologist (board certified or equivalent). An experienced and qualified non-dermatologist physician or experienced medical professional with experience in the conduct of AD clinical trials may be permitted to perform the clinical evaluations of atopic dermatitis when designated by the primary site Investigator. The evaluator must receive and

document protocol specific and applicable efficacy assessment scales training prior to performing these evaluations. **To assure consistency and reduce variability, the same evaluator must assess all dermatological clinical evaluations for any individual subject throughout the study whenever possible;** a back-up experienced and qualified, protocol-trained evaluator will only be allowed and documented in case of emergency or special situations when the designated evaluator is unable to perform the evaluation.

7.6.2. Investigator’s Global Assessment (IGA)

The Investigator’s Global Assessment of atopic dermatitis is scored on a 5-point scale (0-4), reflecting a global consideration of the erythema, induration and scaling. The clinical evaluator of atopic dermatitis will perform an assessment of the overall severity of atopic dermatitis and assign an IGA score and category as described in Table 3. The assessment will be a static evaluation without regard to the score at a previous visit.

Table 3. Investigator’s Global Assessment (IGA) Score

Score	Category	Description*
0	Clear	Atopic dermatitis is cleared, except for any residual discoloration (post-inflammatory hyperpigmentation and/or hypopigmentation).
1	Almost Clear	Overall, the atopic dermatitis is not entirely cleared and remaining lesions are light pink (not including post inflammatory hyperpigmentation) and/or; have barely palpable hard thickened skin and/or papules and/or; have barely perceptible lichenification; excoriation and oozing/crusting are absent.
2	Mild	Overall, the atopic dermatitis consists of lesions that are light red; with slight, but definite hard thickened skin and/or papules; with slight, but definite linear or picked scratch marks or penetrating surface injury; with slight, but definite thickened skin, fine skin markings, and lichenoid scale; oozing/crusting is absent.
3	Moderate	Overall, the atopic dermatitis consists of lesions that are red; with easily palpable moderate hard thickened skin and/or papules; with moderate linear or picked scratch marks or penetrating surface injury; with moderate thickened skin, coarse skin markings, and coarse lichenoid scale; with slight oozing/crusting.
4	Severe	Overall, the atopic dermatitis consists of lesions that are deep, dark red; with severe hard thickened skin and/or papules; with severe linear or picked scratch marks or penetrating surface injury; with severe thickened skin with very coarse skin markings and lichenoid scale; with moderate to severe oozing/crusting.

* The IGA will exclude scalp, palms, and soles from the assessment/scoring.

7.6.3. Eczema Area and Severity Index (EASI)

The EASI quantifies the severity of a subject’s atopic dermatitis based on both severity of lesion clinical signs and the percent of BSA affected. EASI is a composite scoring by the atopic dermatitis clinical evaluator of the degree of erythema, induration/papulation, excoriation, and lichenification (each scored separately) for each of four body regions, with adjustment for the percent of BSA involved for each body region and for the proportion of the body region to the whole body.

090177e1912f28afApproved\Approved On: 26-Jun-2019 09:23 (GMT)

Lesion Severity by Clinical Signs: The basic characteristics of atopic dermatitis lesions-erythema, induration/papulation, excoriation, and lichenification-provide a means for assessing the severity of lesions. Assessment of these four main clinical signs is performed separately for four body regions: head and neck, upper limbs, trunk (including axillae and groin) and lower limbs (including buttocks). Average erythema, induration/papulation, excoriation, and lichenification are scored for each body region according to a 4 point scale: 0 = absent; 1 = mild; 2 = moderate; 3 = severe. Morphologic descriptors for each clinical sign severity score are shown in Table 4.

Table 4. Clinical Sign Severity Scoring Criteria for the Eczema Area and Severity Index (EASI)

Score		Description*
Erythema (E)		
0	Absent	None; may have residual discoloration (post-inflammatory hyperpigmentation and/or hypopigmentation)
1	Mild	Light pink to light red
2	Moderate	Red
3	Severe	Deep, dark red
Induration/Papulation (I)		
0	Absent	None
1	Mild	Barely palpable to slight, but definite hard thickened skin and/or papules
2	Moderate	Easily palpable moderate hard thickened skin and/or papules
3	Severe	Severe hard thickened skin and/or papules
Excoriation (Ex)		
0	Absent	None
1	Mild	Slight, but definite linear or picked scratch marks or penetrating surface injury
2	Moderate	Moderate linear or picked scratch marks or penetrating surface injury
3	Severe	Severe linear or picked scratch marks or penetrating surface injury
Lichenification (L)		
0	Absent	None
1	Mild	Barely perceptible to slight, but definite thickened skin, fine skin markings, and lichenoid scale
2	Moderate	Moderate thickened skin, coarse skin markings, and coarse lichenoid scale
3	Severe	Severe thickened skin with very coarse skin markings and lichenoid scale

* The EASI will exclude scalp, palms, and soles from the assessment/scoring.

Percent BSA with Atopic Dermatitis: The number of handprints of skin afflicted with atopic dermatitis in a body region can be used to determine the extent (%) to which a body region is involved with atopic dermatitis (Table 5). When measuring, the handprint unit refers to the size of each individual subject's hand with fingers in a closed position.

Table 5. Handprint Determination of Body Surface Area (BSA)

Body Region	Total Number of Handprints in Body Region*	Surface Area of Body Region Equivalent of One Handprint*
Head and Neck	10	10%
Upper Limbs	20	5%
Trunk (including axillae and groin/genitals)	30	3.33%
Lower Limbs (including buttocks)	40	2.5%

Handprint refers to the hand size of each individual subject.

* The number of handprints will be for the entire body region; these values will not be adjusted for exclusion of scalp, palms, and soles from the BSA assessment.

The extent (%) to which each of the four body regions is involved with atopic dermatitis is categorized to a numerical Area Score using a non-linear scaling method according to the following BSA scoring criteria (Table 6).

Table 6. Eczema Area and Severity Index (EASI) Area Score Criteria

Percent BSA with Atopic Dermatitis in a Body Region	Area Score
0%	0
>0 - <10%	1
10 - <30%	2
30 - <50%	3
50 - <70%	4
70 - <90%	5
90 - 100%	6

Body Region Weighting: Each body region is weighted according to its approximate percentage of the whole body (Table 7).

Table 7. Eczema Area and Severity Index (EASI) Body Region Weighting

Body Region	Body Region Weighting
Head and Neck	0.1
Upper Limbs	0.2
Trunk (including axillae and groin/genitals)	0.3
Lower Limbs (including buttocks)	0.4

* No adjustment for body regions excluded for assessment

090177e1912f28afApproved\Approved On: 26-Jun-2019 09:23 (GMT)

In each body region, the sum of the Clinical Signs Severity Scores for erythema, induration/papulation, excoriation, and lichenification is multiplied by the Area Score and by the Body Region Weighting to provide a body region value, which is then summed across all four body regions resulting in an EASI score as described in Equation 3.

Equation 3:
$$\text{EASI} = 0.1A_h(E_h+I_h+Ex_h+L_h) + 0.2A_u(E_u+I_u+Ex_u+L_u) + 0.3A_t(E_t+I_t+Ex_t+L_t) + 0.4A_l(E_l+I_l+Ex_l+L_l)$$

A = Area Score; E = erythema; I = induration/papulation; Ex = excoriation; L = lichenification; h = head and neck; u = upper limbs; t = trunk; l = lower limbs

The EASI score can vary in increments of 0.1 and range from 0.0 to 72.0, with higher scores representing greater severity of atopic dermatitis.

7.6.3.1. Body Surface Area – Efficacy (BSA Efficacy)

BSA Efficacy will be derived from the sum of the BSA in handprints across 4 body regions assessed as part of the EASI assessment (Table 5). Handprint refers to that of each individual subject for their own measurement. The BSA Efficacy ranges from 0 to 100%, with higher values representing greater severity of atopic dermatitis. Since the scalp, palms, and soles will be excluded from the BSA (Efficacy) assessment, the maximum possible value will be less than 100%.

7.6.4. Scoring Atopic Dermatitis (SCORAD)

SCORAD is a validated scoring index for atopic dermatitis, which combines extent (0-100), severity (0-18), and subjective symptoms (0-20) based on pruritus and sleep loss, each scored (0-10).

Extent (A, maximum score of 100%)

To determine extent of AD, rule of 9 is used to calculate body surface area affected by AD as a percentage of the whole body surface area. Body surface area as percentage of total body surface area for each body region is as follows:

- Head and neck 9%;
- Upper limbs 9% each;
- Lower limbs 18% each;
- Anterior trunk 18%;
- Back 18%;
- 1% for genitals.

The score for each body region is added up to determine the BSA affected by AD (A), which has a possible maximum score of 100%.

Severity (B, maximum score of 18)

A representative area of AD is selected. In this area, the severity of each of the following signs is assessed as none (0), mild (1), moderate (2) or severe (3):

- Erythema (reddening);
- Edema (swelling)/papulation;
- Oozing/crusting;
- Excoriation (scratch marks);
- Skin thickening (lichenification);
- Xerosis (dryness) (this is assessed in an area where there is no inflammation).

The severity scores are added together to give 'B' (maximum score of 18).

Subjective Symptoms (C, maximum score of 20)

Subjective symptoms (ie, itch and sleep loss) are each scored by the subject using a visual analog scale (VAS) where “0” is no itch (or no sleep loss) and “10” is the worst imaginable itch (or sleep loss). The value for each should reflect the average on a 10 point scale for the last 3 days/nights. These scores are added to give 'C' (maximum score of 20).

SCORAD Total Score

The SCORAD for an individual is calculated by the formula: $A/5 + 7B/2 + C$ (can range from 0 to 103).

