6.2.3. Visit 4, Day 15/Week 2 (± 1 day)

- Administer PROs including PtGA, DLQI (or CDLQI), POEM, HADS and EQ-5D-5L (or EQ-5D-Y);
- Adolescents 12-17 years of age will complete the CDLQI instead of the DLQI and the EQ-5D-Y instead of the EQ-5D-5L;
- Review pruritus NRS and PSAAD completion (in selected countries) and review eDiary procedures with subject as necessary. Instruct subject that pruritus NRS will now be completed only at visits on site and in the eDiary and will no longer be completed on a daily basis at home;
- Urine pregnancy test (female subjects of childbearing potential, including adolescents aged 12 years and older, regardless of whether they have experienced menarche). A negative urine pregnancy test must be obtained prior to dosing with the investigational product;
- Administer investigational product at clinic;
- Perform a single 12-lead electrocardiogram (ECG);
- Conduct targeted physical examination;
- Obtain samples for laboratory testing: serum chemistry, hematology (including coagulation panel), and urinalysis;
- Conduct clinical evaluations including IGA, SCORAD, EASI and BSA (calculated in the EASI);
- Obtain vital signs including pulse rate, sitting blood pressure, respiratory rate and oral or tympanic temperature (after at least 5 minutes of rest). Vital signs must be performed at least 1 hour following administration of investigational product;
- Assess need for contraception and adherence to applicable lifestyle requirements (Section 4.4). Establish willingness and ability to comply with lifestyle requirements going forward in the study;
- Review any changes in the subject's concomitant medications and treatments information;
- Review eDiary to assess completion;
- Perform drug accountability procedures;
- Assess and record any Adverse Events since the last visit.

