7.7. Patient-reported Outcomes (PROs)

Subjects will complete the PROs at the clinic prior to other clinical activities and investigational product administration. The PROs should be checked for completeness by the study site staff before proceeding with other steps of the clinical visit procedures. Compliance with scheduled PROs activities will be monitored. Delegated site staff will oversee the administration of PROs at site visits to ensure protocol compliance. Subjects are given a handheld device to complete the Pruritus NRS and PSAAD according to the [Schedule of Activities](#). Delegated site staff will review compliance at each visit and counsel as appropriate. If a subject has repeated non-compliance, the subject should be re-trained on the device. If a subject is unable to complete the PROs on the handheld device due to documented difficulty using the technological devices or other limitation, the subject will be permitted to enter or remain in the study. In the event of electronic malfunction, a replacement device will be shipped to the site.

Examples of the validated paper versions of Patient Reported Outcomes instruments are included in the Appendices of this protocol. In instances where an electronic device is used to collect the PRO data, the electronic version may differ slightly in format or wording compared with the paper version to facilitate electronic implementation.

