7.7.1. Pruritus Numerical Rating Scale (NRS)

Severity of Pruritus

The severity of itch (pruritus) due to atopic dermatitis will be assessed using the Pruritus Numerical Rating Scale, a validated horizontal NRS (Appendix 6).⁴² Subjects will be asked to assess their worst itching due to atopic dermatitis over the past 24 hours on an NRS anchored by the terms “no itch” (0) and “worst itch imaginable” (10). This item will be administered to all subjects. Subjects will enter the pruritus NRS assessment into an eDiary.

Frequency of Pruritus

The frequency of itch (pruritus) due to atopic dermatitis will be assessed using a horizontal NRS (Appendix 6). Subjects will be asked to assess frequency of itching due to atopic dermatitis over the past 24 hours on an NRS anchored by the terms “never/no itching” (0) and “always/constant itching” (10). This item will be administered to all subjects. Subjects will enter the pruritus NRS assessment into an eDiary.

The Pruritus NRS should be completed as per [Schedule of Activities](#).

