This imputation will be repeated multiple times with different MCMC samples to obtain multiple completed datasets. For each such completed dataset, the estimates of the proportions and CMH-weighted difference of proportions between each PF-04965842 dose group and placebo will be obtained along with the associated standard errors using the methods in [Section 5.2.1](#). Rubin’s rule (Rubin, 1987) will be used to combine the multiple estimates and standard errors across the imputed datasets and provide p-values.

The above analysis can be repeated for different combinations of MNAR quantities which will be applied to the probability of response to assess when the conclusion might change (i.e., tipping). Two important scenarios are included in the tipping point analysis framework. When the MNAR quantities are zero and the posterior predictive probabilities in the PF-04965842 dose groups are not shifted, results are obtained under an assumption of MAR for the missing data mechanism. Alternatively, at the other extreme, when the MNAR quantities are 1.0 for each PF-04965842 dose group, results are obtained under an assumption that the distribution of the missing responses after discontinuation of either dose of PF-04965842 is the same as that of the missing responses on the placebo arm. More detailed descriptions are provided in [Appendix 3](#).

Due to a technical error in the process of transmission and collection of electronic data with the device, the data on the pruritus NRS scale was not collected from several subjects at the scheduled visits of Week 2 (Day 15) and after. This was not restricted to a particular site or country and was not indicative of being related to the missing value of pruritus endpoint or any other endpoints. As such, the missing data mechanism may be reasonably assumed to be missing completely at random or missing at random.

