For the binary endpoints derived from the pruritus NRS, a hybrid approach will be used which is partially based on the multiple imputation method described in the previous paragraph. For this analysis, all data missing due to dropouts will be defined as “non-responsive” as described in the first paragraph, but any other data which remains missing at any intermittent visits will be handled using multiple imputation under the MAR assumption (which may be obtained by substituting the MNAR quantities as zero in the analysis described in the previous paragraph; see also, [Appendix 3](#)). At any particular visit, if there are 5 or fewer subjects with missing data in each treatment group after applying the non-responder definition, no imputations will be performed, and the data will remain missing. Note that, as described in the previous paragraphs, the GLMM will be fit to the observed data (i.e., without defining missing data due to dropout as “non-response”).

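### Imputation of missing pruritus NRS4 leaves out the itch VAS taken in SCORAD at the same visit, which costs a little precision at Weeks 4, 8 and 12

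*Protocol*

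**What the plan says.** **The loss.** SAP 5.3.1 reports that, through a technical error with the electronic device, "the data on the pruritus NRS scale was not collected from several subjects at the scheduled visits of Week 2 (Day 15) and after". It gives no count. For the NRS-based binary endpoints, data missing through dropout become non-response, while "any other data which remains missing at any intermittent visits will be handled using multiple imputation under the MAR assumption".

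**The imputation model.** SAP 5.3.1 and Appendix 3 specify a logit-normal GLMM with treatment, visit (Weeks 2, 4, 8 and 12), treatment-by-visit and a subject random intercept. No other outcome enters. Nothing is imputed at a visit with 5 or fewer missing subjects in each group.

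**The itch VAS.** Protocol 7.6.4 says "Subjective symptoms (ie, itch and sleep loss) are each scored by the subject using a visual analog scale (VAS"), from 0 to 10. The Week 2 visit instructs the site to "Conduct clinical evaluations including IGA, SCORAD, EASI and BSA (calculated in the EASI"), and the Week 4, 8 and 12 visits list the same evaluations. SCORAD total, SCORAD50 and SCORAD75 are all analysed at these visits (SAP 6.4.4 and 6.4.6) and cannot be computed without the itch item.

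**The device.** Protocol 7.7 says "Subjects are given a handheld device to complete the Pruritus NRS and PSAAD". SCORAD is not named there. How its VAS is captured is not stated.

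**The role of NRS4.** NRS4 at Weeks 2, 4 and 12 is a key secondary endpoint in the alpha-controlled procedure. Testing stops at the first hypothesis in Sequence A that is not rejected (SAP 5.1).

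**The concern.** The plan draws a missing itch response at random while an itch score from the same subject and visit is probably in the database. For a subject who lost the later NRS values, the model has only the treatment arm and whatever NRS4 that subject has at other visits, through the random intercept. An auxiliary variable that predicts the missing value reduces the between-imputation variance, and with it the Rubin standard error.

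What is at stake is power on alpha-controlled tests. A miss at Week 4 or Week 12 also blocks whatever follows it in Sequence A. The SAP states that the loss was not related to pruritus or to other endpoints, but describes no analysis to support this. The VAS would allow a blinded check, by comparing VAS change in subjects with and without NRS.

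**Working it through.** **1. The plan's own power figures.** Protocol 9.1 has 150 v 75 subjects and two-sided 5%. Power = Φ[(d − 1.96·SE_pooled)/SE_unpooled].

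- IGA 26% v 6%: SE_pooled = √(0.1933 × 0.8067 × 0.02) = 0.0559; SE_unpooled = √(0.26×0.74/150 + 0.06×0.94/75) = 0.0451. Power = 97.8%, against at least 95% stated.
- EASI-75 45% v 15%: SE_pooled = 0.0675, SE_unpooled = 0.0579. Power = 99.8%, against at least 99% stated.
- Joint lower bound: 0.95 + 0.99 − 1 = 0.94, as stated.

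These reproduce. The plan states no response rate, power or missing fraction for NRS4, so everything below rests on assumptions.

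**2. Which visits are exposed.** The NRS is entered daily from Day 1 to Day 15 and afterwards only on visit days (Schedule of Activities, note q). SAP Appendix 2 maps Days 2-22 to Week 2 and keeps the observation closest to Day 15. A diary entry from Days 2-14 can therefore supply Week 2 NRS4 when Day 15 was lost. Weeks 4, 8 and 12 have no such reserve. The relevant pattern is Week 2 observed and a later visit lost.

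**3. Assumptions.** 150 v 75 subjects; NRS4 32% v 15% at Week 12; Week 2 rates 60% of these; latent Week 2-Week 12 correlation 0.5-0.7; NRS-VAS correlation 0.6-0.8; loss completely at random in a fraction f of subjects.

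**4. Formula.** In each arm, Var = p(1−p)/n × [1 + f/(1−f) × (1−R²)]. R² is the share of NRS4 variance explained by what the imputation model knows about the subject. Power = Φ(0.17/SE − 1.96).

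With full data, SE = √(0.32×0.68/150 + 0.15×0.85/75) = √(0.001451 + 0.001700) = 0.0561, and power is 86%.

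Under a normal latent model, one early binary response explains about 6-20% of the variance. Adding the VAS raises this to about 23-48%.

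**5. One combination in full.** Take f = 20%, so f/(1−f) = 0.25, with correlations 0.5 (Week 2-Week 12) and 0.8 (NRS-VAS). Week 2 response alone gives R² of about 0.09 (active) and 0.065 (placebo). With the VAS these become about 0.45 and 0.40.

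- Present model: √(0.001451×1.2275 + 0.001700×1.23375) = 0.0623; power = Φ(2.730 − 1.96) = 77.9%.
- With VAS: √(0.001451×1.1375 + 0.001700×1.15) = 0.0600; power = Φ(2.831 − 1.96) = 80.8%.
- SE falls 3.6%; power rises 2.9 points.

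**6. Over the assumed range.**

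| Missing | Fall in SE | Power gain at two-sided 5% |
|---|---|---|
| 10% | 0.6-1.8% | about 0.5-1.5 points |
| 20% | 1.3-3.7% | about 1-3 points (78-79% to 79-81%) |
| 30% | 2.0-5.6% | about 2-5 points |

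At 2.5%, the level that applies to Sequence A if Week 2 at 200 mg is not rejected, the gain at 20% missing is 1.2-3.6 points.

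**7. Other settings.**

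- Only one visit lost, other visits observed: SE falls 0.3-0.9% at 10% missing and 0.7-1.8% at 20%. These figures also include adding baseline NRS, so the VAS alone gives less.
- No usable NRS4 after baseline: power goes from about 77% to 79-81% at 20% missing, and from about 71% to 74-77% at 30%. Point 2 makes this pattern unlikely.
- Larger effect (45% v 15%): the gain is under 1 point.
- 5 or fewer missing in each group: nothing is imputed, so the gain is nil.

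**The case against.** Four objections carry weight.

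- **Week 2.** A reader might infer that the Week 2 test at 200 mg, which settles whether Sequence A runs at 5% or 2.5%, is the main casualty, and that affected subjects have no data of their own after baseline. The documents do not support this. The daily diary and the Week 2 window usually supply a Week 2 value, and the random intercept carries it forward to later visits.
- **Bias.** A reader might infer that leaving out the VAS biases NRS4. On the SAP's stated premise it does not; MAR does not need the VAS. An analysis counting all missing NRS4 as non-response is also planned (SAP 6.3.1).
- **Size.** The SAP says only that several subjects were affected. A loss of 20-30% of 225 would be 45-68 subjects, which is an assumption. The 5-or-fewer rule could leave nothing to impute. The instruments also differ: for the VAS, "The value for each should reflect the average on a 10 point scale for the last 3 days/nights", whereas the NRS asks for "worst itching due to atopic dermatitis over the past 24 hours". The correlation of 0.6-0.8 is therefore assumed, and only part of the lost precision can return.
- **Capture.** That the VAS survived the device error is inferred from Protocol 7.7. It is not stated anywhere.

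On cost, the present NRS4 missing-data rule came from a revision attributed to blinded data review and FDA input, so changing it needs a documented reason.

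These limit the size of the point but do not remove it. In the likely pattern, a single early binary response says little about Week 12, and the VAS still adds information.

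**Conclusion.** This is a modest efficiency improvement for NRS4 at Weeks 4, 8 and 12. It is neither an error in the plan nor a source of bias under its stated premise. With Week 2 observed and a later visit lost, the gain is about 0.5-1.5 power points at 10% missing, 1-3 at 20% and 2-5 at 30%. That rests on 32% v 15% response, a Week 2-Week 12 correlation of 0.5-0.7, an NRS-VAS correlation of 0.6-0.8 and a two-sided 5% test, none of which the documents give for NRS4. It also depends on the VAS having been captured outside the failed device. The change is worth making because the endpoint is alpha-controlled and the data should already exist.

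**What to change.** Before unblinding:

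1. Confirm how the SCORAD itch VAS was captured, and tabulate missing NRS by visit, blinded (by arm after unblinding).
2. In SAP 5.3.1 and Appendix 3, add same-visit change from baseline in the SCORAD itch VAS as an auxiliary predictor in the NRS4 imputation model. Use it for imputation only and leave the CMH analysis as it stands.
3. Where the VAS is also missing, draw from the present model.
4. Keep the present model as a sensitivity analysis, alongside the planned analysis that counts all missing values as non-response.

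The cost is a SAP wording change with its rationale recorded, and one more covariate in the imputation program. No new data are needed. The downside is a slightly larger imputation model that is specific to NRS4 and no longer identical to the shared Appendix 3 model. If the sponsor prefers to leave the primary rule alone, the VAS-informed imputation can be prespecified as a sensitivity analysis.
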